5.3.4 Missed Doses

If a subject forgets to take a dose on a given day (e.g. the AM dose was not taken), a “make up” dose should not be taken. In general, if more than 4 hours have passed beyond the usual time of day when the dose is taken, that particular dose should not be taken.

5.3.5 Withholding IMP

A “drug holiday” or “dosing break” is not recommended due to the relatively short 28 day period per dose level. However, withholding IMP may be possible under specific conditions. For example, a subject may have a medical event (e.g., dental emergency) that is considered to be transient or reversible within a few days that may potentially have a preferred outcome by withholding IMP. Depending on the specific circumstances, additional days of dosing may be possible to complete a 14 day dosing cycle. The PI or SI should discuss potential events of this nature with the study medical monitor and Sponsor prior to the event if at all possible.

5.3.6 Compliance with IMP

The IMP is to be dispensed by qualified personnel at the study center and only to subjects enrolled in the study. Subject compliance to therapy will be assessed at scheduled study visits by counting the number of tablets returned. Treatment compliance is defined as the subject taking 80% to 120% of the study tablets to be taken during the dosing period for a given dose level. Subjects found to be outside of the definition of compliance may be discontinued from the study at the discretion of the PI or SI.

5.3.7 Blinding

Subjects will be blinded to treatment beginning with the Baseline Lead-in Period that will use placebo tablets that appear identical to ATR-101 125 mg. Dose levels 1 to 5 are split into two weeks of active treatment (ATR-101) followed by two weeks of treatment with matching placebo (Washout Period).

5.3.8 Concomitant Therapies

Use of concomitant treatments should be kept to a minimum during the study. Any therapies given other than IMP (including blood transfusions, parental fluids, and other medications) are to be considered a concomitant medication and must be documented on the electronic case report form (eCRF).

GC and MC are critical concomitant medications used in CAH and will be captured on a separate eCRF from other concomitant therapies.

5.3.9 Glucocorticoid and Mineralocorticoid Replacement for CAH

Subjects must continue to receive GC and MC according to individual regimens established prior to entering the study. The regimen should remain as stable and unchanged as possible to minimize potential confounding effects on efficacy outcome measures. However, changes are permitted to ensure subject safety. It is not expected that ATR-101 will have a direct effect on GC replacement therapy as the GC synthetic pathway is already compromised in CAH. Therefore, decreasing cortisol precursors (i.e. 17-OHP) should have no effect on glucocorticoid requirements over the 14 day ATR-101 treatment period.

The timing of glucocorticoid replacement therapy may have an impact on the measurement of 17-OHP. Replacement steroids (GC and MC) must not be taken on the mornings when adrenal steroids/steroid intermediates are being assessed (i.e. Day 15) as this could confound efficacy endpoint measures. GC and MC replacement doses may be given after blood samples are obtained for laboratory assessments.

Approximately 75% of CAH subjects have deficiency in the mineralocorticoid pathway in addition to the GC pathway.⁵ Thus, the majority of subjects in this study are anticipated to be on MC replacement. ATR-101 inhibition of the MC pathway for these subjects should not have an effect on MC replacement therapy. Subjects that enter the study with sufficiently intact endogenous MC production may be impacted by suppression of this pathway by ATR-101. However, pharmacological doses of GC, especially shorter acting ones such as hydrocortisone, also confer MC activity and the need for replacement MC is not usually required.¹⁴

5.3.10 Prohibited Medications

ATR-101 is metabolized by several cytochrome P450 enzymes (CYPs) including CYP3A4. Concurrent use of drugs known to be metabolized by this pathway should be avoided. (Appendix 4).

ATR-101 is most soluble in acidic conditions. Proton pump inhibitors are prohibited and calcium preparations and antacids should not be used 2 hours before to 2 hours after ATR-101 administration.

Grapefruit and grapefruit juice are known to inhibit CYP3A4. Grapefruit products should be avoided.

Concurrent use of medications that are known to prolong the QT/QTc interval at therapeutic exposures are not permitted while on this protocol (Appendix 3, List A). Drugs that only cause prolonged QT intervals in unusual circumstances (e.g., overdose) may be used with caution (Appendix 3, Lists B and C).

Preclinical data indicate that ATR-101 may compete with certain drugs for P-glycoprotein in the intestinal lumen. The drugs listed in Appendix 5 should be used with caution, as they may have an impact on the level of ATR-101 or vice versa. Note that some of these drugs may also appear in Appendices 3 or 4, and may be contraindicated by those properties.

5.4 Restrictions, Precautions and Warnings

Preclinical studies have identified adrenal suppression with apoptotic histologic changes. Such changes were associated with exposure levels much higher than what is anticipated for this study. However, occurrence of such changes is a possibility. The investigative staff should be familiar with the warnings and precautions for ATR-101 as presented in the Investigator's Brochure.¹⁰

ATR-101 is metabolized by CYP enzymes and is an inhibitor and inducer of CYP enzymes, and as a consequence, ATR-101 may interfere with the metabolism of other medicines also metabolized by CYP, especially CYP3A4. The metabolism of ATR-101 may be affected by other medicines or foods such as grapefruit products that inhibit CYP3A4. Such medicines and grapefruit products must be avoided. ATR-101 is an inhibitor of P-gp and OATP1B1.

Glucocorticoids are CYP substrates so there is the potential for increased GC levels. Glucocorticoid levels will be measured during the course of the study.

5.5 Packaging and Labeling

The formulation and bulk packaging of ATR-101 will be conducted according to standard procedures. The IMP will be packaged and labeled by the Sponsor's designated contract packager and labelled according to regulatory requirements. IMP will be provided to sites as kits containing a total of 15 bottles. Each kit will provide both ATR-101 and matching placebo for the Baseline Lead-in Period as well as Dose Levels 1-5.

5.6 Storage and Accountability

Study drug must be kept in a secured location and stored at controlled room temperature at the study site within its original container. A daily temperature log for monitoring of proper storage conditions must be maintained by the site.

Access to drug must be restricted to designated study personnel only. Under no circumstances should the PI/SI or site personnel supply study product to other Investigators or clinics, or allow the supplies to be used other than as directed by this protocol without written authorization from the Sponsor. The PI (or delegate) must maintain records of the delivery of the study drug to the study site, the inventory at the site, use for each subject, and return of the study drug to a delegate of the Sponsor or destruction. Total study site accountability will be conducted at the end of the study and the PI/SI (or delegate) must explain all discrepancies. A Site Drug Accountability Log will be supplied by the Sponsor. This log must be kept current and should contain the following information:

- Identification (subject ID number and initials) of subject to whom the study drug was dispensed
- The dates and kit numbers for dispensed study drug
- Initial inventory on receipt of drug at the site
- Final inventory on completion of the study

All records and inventory must be available for inspection by the clinical study monitor. Additional details on the storage and handling of ATR-101 will be provided in the Pharmacy Manual.

5.7 Investigational Product Retention at Study Site

At the time of study close-out, the Sponsor will direct the site regarding the disposition of any unused IMP whether it is to be destroyed or be returned to the Sponsor's designated location. The Sponsor will assure that a final report of drug accountability is prepared and maintained by the investigative site. Additional details on the inventory of IMP will be provided in the Pharmacy Manual.

6 STUDY PROCEDURES

6.1 Allowable Variation in Study Visits

Visits and the protocol defined days for each specific period/procedure should be adhered to as much as possible. However, there is flexibility to allow for logistical considerations and to accommodate scheduling conflicts. Variations to the protocol defined visit dates (i.e. study days) may be allowed depending upon the specific circumstances.

- Screening Visit. Up to 21 days.
- Baseline Lead-in Period. A minimum of 14 days must be completed but an additional 3 days beyond the 14 day period is allowed.
- Dose Levels 1-5
 - ATR-101 Treatment Period
 - A minimum of 11 days (22 doses) of ATR-101 must be taken prior to drawing blood samples for an assessment of efficacy and safety. Therefore, sample collection cannot occur earlier than the 12th day of dosing for a given dose level.
 - A maximum of + 3 days is allowed beyond the scheduled 14 day ATR-101 treatment period.
 - Placebo Washout Period
 - A minimum of 11 days (22 doses) of placebo must be taken prior to drawing blood samples for an assessment of efficacy and safety. Therefore, sample collection cannot occur earlier than the 12th day of dosing for a given dose level.
 - A maximum of + 3 days is allowed beyond the scheduled 14 day placebo treatment period.
- Follow-up visit. A window of ± 3 days is permitted.

6.2 Informed Consent

Prior to any study specific screening evaluations and clinical trial participation, written informed consent will be obtained from each subject to be involved in the clinical trial by using the Institutional Review Board/Independent Ethics Committee (IRB/IEC) approved ICF. Potential subjects will be informed in detail about the study product to be administered, and the nature of the clinical investigation with its risks and discomforts to be expected. The subjects will also be instructed that they are free to withdraw their consent and discontinue participation in the clinical trial at any time. The PI/SI will verify that the subject has granted consent. Each subject will be given a copy of the signed ICF. Certified translated ICFs will be provided by the Sponsor in those languages required or requested by investigational sites.

6.3 Eligibility

Review of study inclusion/exclusion criteria will be done at the Screening visit, at the start of the Baseline Lead-in Period and reconfirmed prior to receiving the first dose of IMP (Dose Level 1). Noncompliance with IMP (i.e., not meeting 80-120%) during the Baseline Lead-in Period will result in Early Termination from the Study.

6.4 Medical History

A complete medical history will be obtained at the Screening visit. The following systems will be reviewed: head, eyes, ears, nose, and throat (HEENT), respiratory, cardiovascular, gastrointestinal/hepatobiliary (specifically, a history of liver dysfunction or the presence of hepatomegaly or splenomegaly), genitourinary/ reproductive, musculoskeletal, neurological, psychiatric, endocrine/metabolic, blood/lymphatic, dermatologic, and immunologic. Past surgeries will also be recorded.

6.5 Physical Examination

A complete physical examination will be obtained at Screening and the Final Study visit or Early Termination Visit.

An abbreviated (brief) physical exam will be completed as follows:

- Prior to the start of the Baseline Lead-in Period
- Prior to dosing on the first day of every Dose Level (active treatment)
- Prior to starting the placebo Washout Period at each Dose Level

The following systems will be examined for a complete physical examination: HEENT, respiratory, cardiovascular, gastrointestinal/hepatobiliary (specifically the presence of hepatomegaly or splenomegaly will be assessed), genitourinary/ reproductive, musculoskeletal, neurological, psychiatric, endocrine/metabolic, blood/lymphatic, dermatologic, and immunologic. On a brief physical examination, the following systems will be examined: respiratory, cardiovascular, gastrointestinal/hepatobiliary and any areas pertinent to any adverse events.

6.6 Vital Signs

Vital signs, including oral or tympanic temperature, systolic and diastolic blood pressure, pulse, respiratory rate, and body weight will be measured at Screening, at the start of the Baseline Lead-in Period, at Day 1 pre-dose and at 1, 2 and 4 hours post-dose for each dose level, at Day 15 pre-dose for each dose level and at the Final Study Visit or Early Termination Visit. Height will be measured at Screening.

6.7 Electrocardiography and Determination of QTc

All subjects will have 12-lead ECG assessments at Screening, Day 1 pre-dose and 2 hours post-dose for each dose level, Day 15 pre-dose for each dose level, and at the completion of the Placebo Washout Period on Day 29 (this ECG could serve as the pre-dose ECG, Day 1, if the subject is moving to the next dose level or as the ECG for the Final Study Visit or Early Termination Visit). ECGs will be stored for later analysis if needed.

If the QTc is greater than 470 msec on the Screening ECG, three consecutive ECGs will be obtained and the QTc values corrected by the Fridericia method will be averaged. If the average is greater than 470 msec, the subject will be ineligible for the study. In the event of an abnormal ECG (especially in the setting of an intraventricular conduction delay) that makes QTc determination unreliable by standard means, the QT interval will be corrected by the method of Rautaharju et al.¹⁵

6.8 Prior and/or Concomitant Medication Assessments

Prior and concomitant therapies will be documented throughout the study and include any treatments that have been taken within 30 days prior to the first placebo dose in the Baseline Lead-in Period until the Follow-up Visit. Any treatments given during the clinical trial other than IMP, including blood transfusions, parental fluids, herbal preparations, and all pre-medications are considered concomitant therapy and must be recorded on the eCRF. Following completion of the Final Study Visit, only concomitant medications related to follow-up of an AE should be recorded on the eCRF. All prior and concomitant medications will be coded to the latest version of the World Health Organization (WHO) Drug Dictionary.

6.9 Pharmacokinetic Assessments

Blood samples will be collected to profile the levels of ATR-101 and its metabolites at multiple days and times throughout the study. Assessment of ATR-101 levels may help to determine or establish pharmacokinetic and pharmacodynamic relationships. ATR-101 exposure levels may also help in the assessment of safety events. Sampling time points are presented for each of the applicable study days in Table 4. Samples for PK analysis will be taken prior to the first dose of ATR-101 (for each dose level) and up to 4 hours, post-dose. This time period is designed to capture the C_{max} (T_{max} is approximately 2 hours) and a few additional time points. Following the completion of the 14 day ATR-101 dosing period a single PK sample will be collected to assess trough levels of ATR-101 (morning of day 15). Subjects will then enter the 14 day placebo Washout Period. After completion of the placebo Washout period, subjects will either proceed to the next Dose Level and perform the same PK sampling as Day 1, or subjects will complete the Final Study Visit and do the same PK sampling as Day 15.

PK results will not be used to determine dose escalation. Approximately 4 mL of blood will be drawn at each sampling time point.

Table 4 Pharmacokinetic Sampling Time Points.

Visit	Sampling Time Point
Dose Level N, Day 1	Pre-dose, post-dose at 1, 2, 3, and 4 hours
Dose Level N, Day 15	Pre-dose, single blood draw

N=Dose Levels 1-5

6.10 Pharmacodynamic Assessments

The effects of ATR-101 on adrenal steroid synthesis will be assessed at each study visit by measuring steroids and steroid intermediates across the mineralocorticoid, glucocorticoid and androgen pathways. Plasma renin activity (PRA) is not an adrenal steroid, but it will be measured as an assessment of mineralocorticoid activity. In addition, ACTH levels will be assessed to determine the potential impact on the HPA-axis.

Pharmacodynamic measures:

- Glucocorticoid pathway: 17-OHP, progesterone
- Mineralocorticoid pathway: 11-deoxycorticosterone (11-DOC); PRA; aldosterone
- Androgens: androstenedione, total testosterone, free testosterone, DHEA, DHEA-S
- HPA-axis: ACTH

6.11 Timing of Pharmacodynamic Blood Samples and Dosing of Replacement Steroids

Adrenal steroids and steroid intermediates have a diurnal rhythmicity with peak 17-OHP occurring at around 8:00 AM. Thus, it is extremely critical that the timing of sample collection for efficacy endpoints and dosing of replacement steroids be precise and consistent. Every attempt should be made to collect the sample between 8:00-9:00 AM, but no later than 10:00AM. Study visits that require blood sample collection for steroid hormones, must adhere to the following:

- Morning dose of replacement GC and MC must not be given until after the blood sample is collected
- Blood sample collection must be done prior to **10:00 AM**

If both of these conditions are not met, the blood sample for steroid hormones must not be collected; the visit procedures should not be performed and the study visit must be rescheduled for the next day or as soon as feasible. The subject should continue taking study drug with the last dose occurring the evening prior to the rescheduled visit.

Dosing of GC and MC may take place after collection of blood samples for adrenal steroids and steroid intermediates.

Approximately 20 mL of blood will be collected for steroid hormone testing and approximately 10 mL of blood will be collected for testing synthetic glucocorticoid levels. If exogenous GC levels are suspected of confounding the efficacy outcome measures, additional testing may be performed. Further details on sample collection and handling are provided in the Laboratory Manual.

6.12 Adverse Events, Serious Adverse Events, and Reporting

6.12.1 Adverse Events, Severity, and Relationship

Adverse Event (AE): Any untoward medical occurrence in a subject or clinical investigation subject administered an investigational product. An AE does not necessarily have a causal relationship with IMP.

- All AEs reported for enrolled subjects during the clinical study will be recorded on the eCRF. All AEs, regardless of relationship to study drug or procedure, should be collected beginning from the time the subject signs the study consent. AEs in clinical investigation subjects include any change in the subject's condition. This includes symptoms, physical findings, or clinical syndromes.
- An abnormal laboratory value may be considered an AE if the identified laboratory abnormality leads to any type of intervention whether prescribed in the protocol or not. It is up to the PI/SI to determine whether an abnormal laboratory value constitutes an AE. If an abnormal laboratory value is caused by a disease process, the disease process and not the laboratory abnormality should be listed as the AE (e.g., if new onset viral hepatitis is causing elevated alanine aminotransferase (ALT), hepatitis and not the elevated ALT should be listed as the AE).
- Examples of laboratory abnormalities that should be considered AEs include those that result in withdrawal of the study treatment, withholding study treatment pending some investigational outcome, or additional concomitant treatment. All laboratory abnormalities considered to constitute an AE should be recorded on the appropriate AE page of the eCRF. Laboratory abnormalities do not need to be listed as separate AEs if they are considered to be part of a clinical syndrome that is being reported as an AE. It is the responsibility of the Investigator to review all laboratory findings in all subjects. Abnormal values should be commented upon as to clinical relevance or importance on the eCRF or the laboratory report as appropriate. Medical and scientific judgment should be exercised in deciding whether an isolated laboratory abnormality should be classified as an AE.
- AEs will be collected from the time the subject signs informed consent until 30 days after last dose of IMP.
- Every effort must be made by the PI/SI to categorize each AE according to its severity and its relationship to IMP.
- Subjects who develop toxicity on study will be followed until the event resolves, stabilizes or returns to baseline.

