- ^k Obtained for females of childbearing potential who are not surgically sterile or who have not been naturally postmenopausal for at least 12 consecutive months (i.e., who have had menses any time in the preceding 12 consecutive months). A serum pregnancy test will be performed at Screening. A urine pregnancy test will be performed prior to dosing on Day 1 of each Dose Level and at the Final Study Visit or Early Termination Visit.
- ^l Blood for PK analysis of ATR101 and its metabolites in plasma will be obtained on Day 1 of each Dose Level at pre-dose and 1, 2, 3, and 4 hours post-dose; on Day 15 of each Dose Level at pre-dose and at the Final Study Visit or Early Termination Visit. A window of \pm 10 minutes is permitted around each sampling time-point.
- ^m The first dose will be administered on site on Day 1 and Day 15 of each dose level.
- ⁿ All bottles and unused tablets must be returned to the study site on Day 1 and Day 15 of each dose level and at the Final Study Visit or Early Termination Visit.
- ^o IMP compliance will be assessed by counting the number of tablets returned and determining if the correct number were taken within the window of 80% to 120%.
- ^p AEs will be collected from the time the subject signs the informed consent form until 30 days after the last dose of IMP.
- ^q Tests do not need to be repeated on Day 1 of Baseline Lead-In if the subject's clinical condition has not changed and these tests were done \leq 14 days prior to Day 1

TABLE OF CONTENTS

Synopsis	2
Table Of Contents	8
LIST OF IN-TEXT TABLES	11
LIST OF IN-TEXT FIGURES.....	11
LIST OF APPENDICES.....	12
List of Abbreviations	13
1 Introduction.....	15
1.1 Description of Congenital Adrenal Hyperplasia.....	15
1.2 Rationale for Use of ATR-101 in Congenital Adrenal Hyperplasia.....	16
2 Study Objectives	17
2.1 Primary Objective	17
2.2 Secondary Objectives	17
3 Investigational Plan.....	18
3.1 Overall Study Design and Plan.....	18
3.1.1 Screening Period	20
3.1.2 Baseline Lead-in Period.....	20
3.1.3 Dose Level 1 (ATR-101 125 mg BID and matching placebo).....	20
3.1.4 Dose Levels 2, 3, 4 and 5.....	21
3.1.5 Final Study Visit	21
3.1.6 Follow-up Visit	21
3.2 Rationale for Study Design and Dose Levels	21
3.3 Efficacy Assessment.....	23
3.4 Safety Assessment	23
4 Study Population Selection.....	24
4.1 Study Population.....	24
4.2 Inclusion Criteria	24
4.3 Exclusion Criteria	25
5. Study Treatment.....	26
5.1 Assignment of Subject Identification Numbers.....	26

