3.1.6 Follow-up Visit

Two weeks after the Final Study Visit or Early Termination Visit, a Follow-up Visit will take place. This will consist of a telephone interview with the subject to determine if any safety events need to be reported and to record concomitant medications, especially GC and MC.

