6.12.5.2 Reporting Serious Adverse Events (SAEs)

Initial Reports

All SAEs occurring from the time of informed consent through the early termination/final visit and for 30 days following study drug discontinuation, whichever is longer, must be reported to Medpace Clinical Safety **within 24 hours** of the knowledge of the occurrence (this refers to any adverse event that meets any of the aforementioned serious criteria). All serious adverse events that the investigator considers related to study drug occurring after the 30-day follow-up period must be reported to the Sponsor.

To report the SAE, complete the SAE form electronically in the electronic data capture (EDC) system for the study. When the form is completed, Medpace Safety personnel will be notified electronically and will retrieve the form. If the event meets serious criteria and it is not possible to access the EDC system, send an email to Medpace Safety at [contact] or call the Medpace SAE hotline (phone number listed below), and fax the completed paper SAE form to Medpace (fax number listed below) within 24 hours of awareness. When the EDC system becomes available, the SAE information must be entered within 24 hours of the system becoming available.

Safety Contact Information:

Medpace Clinical Safety
Medpace SAE hotline – USA:
[contact], ext. 2999 **or** [contact], ext. 2999
[contact] **or** [contact]
e-mail: [contact]

Follow-Up Reports

The investigator must continue to follow the subject until the SAE has subsided or until the condition becomes chronic in nature, stabilizes (in the case of persistent impairment) or the subject dies.

Within 24 hours of receipt of follow-up information, the investigator must update the SAE form electronically in the EDC system for the study and submit any supporting documentation (e.g., subject discharge summary or autopsy reports) to Medpace Clinical Safety via fax or e-mail. If it is not possible to access the EDC system, refer to the procedures outlined above for initial reporting of SAEs.

The Investigator should notify the IRB/ IEC of the occurrence of the SAE, in writing, in accordance with local requirements. A copy of this communication must be forwarded to the clinical research associate (CRA) and filed in the trial master file (TMF).

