7.8 Follow-up Visit

Two weeks after completion of the Final Study Visit or Early Termination Visit, the PI, SI or other qualified medical personnel from the study center will contact the subject. A telephone interview will take place to confirm the status of the subject. Any safety events will be reported and concomitant medications, including replacement steroids will be recorded. This telephone interview will conclude the subject's study participation.

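### AE and SAE windows run to 30 days after the last dose, but the last scheduled contact is a call 14 ± 3 days after the final or early termination visit

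*Protocol*

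**What the plan says.** The window appears in three places in the protocol.

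- 6.12.1: "AEs will be collected from the time the subject signs informed consent until 30 days after last dose of IMP".
- Schedule of Assessments, footnote p: "AEs will be collected from the time the subject signs the informed consent form until 30 days after the last dose of IMP".
- 6.12.5.2: SAEs are reportable from consent through the final or early termination visit and "for 30 days following study drug discontinuation, whichever is longer".

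The last contact is set elsewhere.

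- 3.1.6: "Two weeks after the Final Study Visit or Early Termination Visit, a Follow-up Visit will take place". It is a telephone interview, meant to find out whether there are safety events to report.
- 7.8 repeats the timing ("Two weeks after completion of the Final Study Visit or Early Termination Visit, the PI, SI or other qualified medical personnel") and adds: "This telephone interview will conclude the" subject's participation.
- 6.1: "Follow-up visit. A window of ± 3 days is permitted".

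The AE row of the schedule ends at that call.

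The date of the Early Termination Visit is not stated consistently. Sections 6.15 and 7.7 give no interval between withdrawal and the visit. The schedule's column header and 6.13 label the visit Day 29, and 6.7 lets the Day 29 ECG serve for it.

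**The concern.** A 30-day rule and a schedule that closes at about two weeks do not fit together, and the protocol does not say which one governs. After the call, a new non-serious event reaches the database only if the subject volunteers it.

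The group in which this could matter is subjects who stop while taking ATR-101, because no placebo washout need separate their last active dose from their last visit. Section 5.3.3 recommends early termination when a dose is not tolerated for a safety reason, so this group includes tolerability failures. Safety is part of the primary objective, there is no DSMB (10.7), and accrual is capped at 17 subjects.

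The clock itself is also unclear. Two of the three statements start it at the last IMP dose, and the SAE rule starts it at study drug discontinuation. Placebo is mostly treated as IMP: 7.3 dispenses IMP for the washout days, and 6.3 speaks of IMP noncompliance in the lead-in. Yet 6.3 also calls Dose Level 1 the first IMP dose.

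**Working it through.** **Inputs**

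- Window: 30 days (6.12.1, footnote p, 6.12.5.2).
- Call: *c* = 11, 14 or 17 days after the visit (3.1.6 and 7.8, with ± 3 days from 6.1).
- Last ATR-101 dose of a dose level: evening of Day 14 (3.1.3).
- Washout: *w* = 14 days nominally. The minimum is 11 (6.1: "A minimum of 11 days (22 doses) of placebo must be taken prior to drawing blood samples") and the maximum is 14 + 3 = 17.
- Lag *k*: days from the reference dose to the visit.

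**The plan's own calendar.** 14 days of ATR-101 + 14 days of placebo + 1 = Day 29, which matches the labelled final visit.

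**Formula.** Days of the window after the last scheduled contact = max(0, 30 − (*k* + *c*)).

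| Case | *k* | Call, days after the dose | Uncovered: nominal (range) |
|---|---|---|---|
| Completer, from last placebo tablet (Day 28) | 1 | 12, 15, 18 | 15 (12 to 18) |
| Completer, from last ATR-101 dose, *w* = 14 | 15 | 26, 29, 32 | 1 (0 to 4) |
| Same, *w* = 11 | 12 | 23, 26, 29 | 4 (1 to 7) |
| Same, *w* = 17 | 18 | 29, 32, 35 | 0 (0 to 1) |
| Stops on ATR-101, visit next morning | 1 | 12, 15, 18 | 15 (12 to 18) |
| Stops on ATR-101, visit 7 days later (assumed lag) | 7 | 18, 21, 24 | 9 (6 to 12) |
| Last ATR-101 dose Day 14, visit Day 29 | 15 | 26, 29, 32 | 1 (0 to 4) |
| Last ATR-101 dose Day 13, visit Day 29 | 16 | 27, 30, 33 | 0 (0 to 3) |
| Last ATR-101 dose Day 10, visit Day 29 | 19 | 30, 33, 36 | 0 |

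For completers in calendar days, the window from the last placebo tablet closes on Day 28 + 30 = 58, and the nominal call is on Day 29 + 14 = 43. The difference is 15 days. From the last ATR-101 dose the window closes on Day 14 + 30 = 44, one day after the call.

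For a subject who stops during an ATR-101 period, the result depends on which statement of the visit date applies. A next-morning visit fits the procedures in 7.7, which call for steroid sampling before 10 AM and a trough PK sample. Section 6.9 makes final-visit PK sampling the same as Day 15, which is pre-dose. The Day 29 label gives a lag of 29 − *d* for a last dose on Day *d*, so the earlier the subject stops, the smaller the gap.

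**The case against.** **A collection window is not a promise of scheduled questioning.** Section 6.12.1 says until when AEs are collected, and the SAE clock in 6.12.5.2 runs from the site's knowledge of the event. Known toxicity is followed until it resolves, stabilises or returns to baseline. SAEs are followed to outcome, and related SAEs stay reportable after 30 days. This stands, and it confines the loss to new events that are not spontaneously reported. It does not remove the conflict, because the same protocol ends participation at the call, and 3.1.6 relies on that call to find safety events.

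**Day 29.** If the printed label governs, the gap after stopping ATR-101 nearly vanishes. Section 7.7 can equally be read as allowing an earlier visit. Neither reading can be excluded, so both results are given.

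**Completers.** Their 15 days run from a placebo tablet. Counted from ATR-101 the nominal gap is 1 day, so the practical effect on ATR-101 safety is small. This stands.

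**Stronger readings a reader might infer.**

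- Early stoppers could go unquestioned for 19 of the 30 days. That needs a visit on the day of the last dose and a call at the early edge of its window (30 − 11 = 19). A same-day visit fits poorly with the morning and trough sampling in 7.7.
- The protocol gives no date at all for the Early Termination Visit. It gives one, Day 29, which sits uneasily with 6.15 and 7.7.
- ATR-101 events are under-counted in completers. SAP 6.11.1 assigns events that start after the first washout dose to Placebo, so the completers' gap does not support this.
- The SAP's lack of a TEAE end date loses late events. It does not, because a late event that is reported still counts. The SAP simply leaves the length of the period open.

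**Conclusion.** The mismatch between a 30-day collection rule and participation that ends at the call is certain from the text. Its size depends on the reference dose and the visit date.

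- Completers: nominally 15 days (12 to 18) from the last IMP dose, and nominally 1 day (0 to 7) from the last ATR-101 dose.
- Subjects who stop during an ATR-101 period: nominally 15 days (12 to 18) if seen the next morning, and nominally at most 1 day (0 to 4) if seen at Day 29.

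The Day 29 figure assumes that the last ATR-101 dose is no later than the scheduled Day 14. Confidence in the mismatch is high. Confidence in the size of the early-stopper gap is moderate, because the protocol contradicts itself on the date. The documents give no expected number of early terminators, so no count of missed events can be derived. The primary endpoint is not touched. This is a modest safety-ascertainment point that is cheap to correct.

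**What to change.** 1. Reconcile footnote p, 6.12.1 and 6.12.5.2 with 3.1.6, 6.1 and 7.8, using one term for the dose (last IMP or last ATR-101) that starts the 30-day clock.
2. Reconcile the Day 29 label (schedule header, 6.7, 6.13) with 6.15 and 7.7, so that the interval from last dose to Early Termination Visit is stated once.
3. Time the closing telephone contact at or after the end of the stated window, or keep the two-week call and add one brief call there. At minimum, do this for subjects who stop during an ATR-101 period.
4. If the contact stays as it is, restate the AE and SAE window as the period actively ascertained.

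The cost is a small wording amendment. Retiming the call adds about two weeks of participation (nominally 15 days after a next-morning early termination visit) and gives up the two-week contact. Keeping both costs one extra call per affected subject. Restating the window needs no extra contact but shortens the stated safety window.
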